6.4 STUDY INTERVENTION COMPLIANCE

Compliance with study drug dosing will be assessed during on-site visits, at study day 28, 56, 84, 112, 140, 168 visits as well as unscheduled visits, if required. Participants will be asked to bring their bottles of study drug for a recorded pill count. Participants who have demonstrated less than 80% compliance at study visits will be withdrawn from the study. Compliance with study medication will be determined by the PI based on multiple factors, including but not limited to pill count, overall compliance with study procedures, and the reliability of self-reporting of compliance based on prior interactions. Study treatment compliance will also be assessed on telephone calls on day 7, 21, 42, 70, and 154 (+/- 3 days). A standard scripted conversation will be used for telephone calls to determine compliance with protocol requirements. Participants withdrawn from the study after receiving study treatment will be asked to follow up to complete the study days 168 and 196.

6.5 MISSING STUDY MEDICATION

Doses and loss of medication bottle are possible occurrences during the 24-week (168 day) dosing period. Missed doses will be documented at each compliance check but will not result in a protocol deviation. In the event a dispensed bottle of study drug is lost by a participant, the study team will contact pharmacy and dispense a replacement bottle to the participant. A note to file will be created describing the event in detail and the incident will be reported to Pfizer. In the event the missing study drug is found, participants will be advised to return it.

6.6 CONCOMITANT THERAPY

For this protocol, a prescription medication is defined as a medication that can be prescribed only by a properly authorized/licensed clinician. Medications to be reported in the Case Report Form (CRF) are concomitant prescription medications, over-the-counter medications and supplements.

Concomitant therapy information will be recorded at all study visits including screening.

Abbreviated Title: Tofacitinib in Sjögren's syndrome

Version Date: 07/01/2024

The following medications are allowed provided that they are administered at stable doses during the study:

- Antimalarial (hydroxychloroquine 400 mg/day or \leq 6.5 mg/kg/day, if more than 400 mg/day, chloroquine phosphate 500 mg daily, quinacrine 100 mg daily); must already be on stable dose of this medication 12 weeks (96 days) prior to study entry.
- Prednisone or equivalent steroid dose up to 10 mg /day must already be on stable dose of this medication four (4) weeks (28 days) prior to study entry.
- ACE (angiotensin converting enzyme) inhibitors or angiotensin receptor blocking (ARB) medications, must already be on stable dose of this medication four (4) weeks (28 days) prior to study entry.
- Prescription medications with oral drying as a known side effect, such as anti-cholinergic, anti-histamines, selective serotonin reuptake inhibitors, tricyclic anti-depressants, amphetamines, should be stable for 12 weeks (96 days) prior to screening visits.
- Lipid lowering medications if initiated at least three (3) months prior to the screening visit. The dose of any of these medications can be decreased (temporally or for the duration of the study) if clinically indicated for toxicity.

The following systemically administered medications and vaccines listed below will not be allowed during treatment. A list of prohibited medications which will be provided to the participants upon consenting will be reviewed to confirm any of those medications are included in their standard treatment regimen. Local administration of prohibited medications may be allowed in certain circumstances (e.g., Cyclosporine, locally administered corticosteroid injections) at the discretion of the PI or Medically Responsible Investigator. Any clinical indication requiring treatment with medications listed below will lead to cessation of study treatment. Withdrawn participants will be asked to return according to the follow up phase of the study and to complete all study procedures.

- Rituximab.
- Any other biologic agent including TNF- α blockers, IL-1 blocking agents, anti-IL-6 agents, belimumab, abatacept.
- Cyclophosphamide.
- Azathioprine.
- Mycophenolate mofetil.
- Rapamycin.
- Cyclosporine.*
 - Topical cyclosporine used for keratoconjunctival sicca will be permitted.
- Tacrolimus.
- Methotrexate.
- Administration of any live virus vaccines.
- Participants may be on prednisone \leq 10 mg/day at study entry. Prednisone may be increased as indicated after the end of the treatment period on Day 168 (- 7 days). At the investigator's discretion, glucocorticoids may be tapered during the study.
- Any other less common DMARDs

Abbreviated Title: Tofacitinib in Sjögren's syndrome

Version Date: 07/01/2024

The study team will make every attempt for the newly enrolled subjects to receive their COVID-19 vaccine booster from an outside vaccination clinic before randomization. In the event that an enrolled subject requires a vaccine booster during the treatment phase, the study team will make an accommodation of a 1-week interruption of the study drug. The subject will receive the vaccination at their preferred vaccination clinic.

7 STUDY INTERVENTION DISCONTINUATION AND PARTICIPANT DISCONTINUATION/WITHDRAWAL

7.1 DISCONTINUATION OF STUDY INTERVENTION

Discontinuation from study intervention does not mean discontinuation from the study, and remaining study procedures should be completed as indicated by the study protocol. Once enrolled, should study participant evidence a clinically significant finding, the PI or Medically Responsible Investigator will determine if any change in participant management is needed.

An investigator may discontinue study intervention in a participant for the following reasons:

- Completion of study intervention
- Disease progression which requires discontinuation of the study intervention
- If any clinical adverse event (AE), laboratory abnormality, or other medical condition or situation occurs such that continued participation in the study would not be in the best interest of the participant
- Investigator discretion as in Sections 6.4, 6.5 and 7.2
- Positive pregnancy test
- Lymphocyte count less than 500 cells/mm³, confirmed by repeat testing
- ANC less than 500 cells/mm³, confirmed by repeat testing

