6.3 MEASURES TO MINIMIZE BIAS: RANDOMIZATION AND BLINDING

Randomization will be done by the NIH Clinical Research Center Pharmacy in conjunction with the statistician associated with the study. This is a two-arm, double blind study.

The study will utilize the stratified block randomization method to ensure that the Tofacitinib and placebo groups are balanced with respect to the baseline disease activity level. Eligible

Abbreviated Title: Tofacitinib in Sjögren's syndrome

Version Date: 07/01/2024

subjects will be stratified according to the ESSDAI score (0-1 vs. 2-13). Within each stratum, subjects will be randomly assigned by use of computer-generated blocks of size 3 with a 2:1 ratio to Tofacitinib or control group. Thus, participants will be randomized to either Tofacitinib or placebo in a 2:1 ratio overall. Both participants and investigators will be blinded to treatment allocation. Unblinding for analysis will occur once all the collected study data has been entered and the database is locked. Participants and local treating physicians will be informed of treatment allocation by a letter sent by certified mail, at that time.

The blind will be held by the statistician and the NIH Clinical Center Research Pharmacy. In cases where breaking the blind is necessary to provide clinical care to the participant, as determined by the PI and medically responsible team member, [name], the PI will contact the NIH Clinical Center Research Pharmacy and provide the treatment allocation information to the treating physician. Such participant(s) would be withdrawn from the study and followed up as described in section 4.10 above.

The Data and Safety Monitoring Committee (DSMC) may also request unblinding of treatment allocation or group assignment. These requests will be transmitted to the NIH Clinical Center Research Pharmacy by the PI. Data will be provided directly to the DSMC Chair without unblinding the investigators before the DSMC determines a plan of action.

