7.2 PARTICIPANT DISCONTINUATION/WITHDRAWAL FROM THE STUDY

Prior to removal from study, effort must be made to have all subjects complete a safety visit approximately 14 days (+14 days) following the last dose of study therapy. Participants are free to withdraw consent at any time upon request. Participants may also choose to withdraw treatment but remain in the study for follow up. Participants must be withdrawn consistent with Section 6.1.2. Additionally, the PI or Medically Responsible Investigator may also choose to withdraw treatment or withdraw a participant from the study based on clinical or professional judgement. An investigator may withdraw treatment or a participant from study for the following reasons:

- Request by participant to be withdrawn from the study.
- Flares not resolving within 28 days or if, in the opinion of the medically-responsible investigator, the participant requires immediate immunosuppressive therapy that is not allowed in the protocol.
- Any Grade 4 adverse event that is unexpected and at least possibly related to study drug.
- More than 45 days delay in treatment after the screening visit.
- More than one (1) "no-show" for a visit.
- Persistent elevation of LFTs of > 2 times upper limit of normal persistently present on repeated samples 14 days +/- 7 days apart.

- >30% increase in serum creatinine from baseline at enrollment, persistently present on repeated samples 14 days +/- 7 days apart.
- Increase in proteinuria at the time of screening visit to protein to creatinine ratio of more than 1.000 mg/dL or more than 1000 mg in a 24 hours urine collection, persistently present on repeated samples 14 days +/- 7 days apart.
- Any other reason that, in the opinion of the responsible Investigator or Medically Responsible Physician, poses unacceptable risk to the participant.
- Infections requiring intravenous antibiotic treatment.
- Development of any malignancy.
- Urine BK virus level of more than 10 million copies/ml by quantitative PCR or detection of BK virus in serum by quantitative PCR.
- Non-compliance with treatment (<80% compliance by pill count).

The reason for participant discontinuation or withdrawal from the study will be recorded on the Voluntary Study Withdrawal Case Report Form (CRF). Participant who signs informed consent and are randomized, but do not receive the study drug, may be replaced.

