While on this study, participants will continue to receive regular medical care from their primary physicians. Any AEs reported will be followed by the investigators as described in Section 16.1.8. Following completion of the study or after withdrawal from the study, participants will return to the care of their referring physicians. Participants may continue their follow up visits on protocol 15-D-0051 as appropriate. A summary of the participants' course in the study will be sent to the referring physician.

Participants who withdraw or are withdrawn from the study after receiving study treatment will be asked to complete the day 168 and 196 for close out safety assessments. Participants are deemed ineligible before study day 1 or randomization will resume care with their referring physician with no further evaluation in this protocol.

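### The protocol does not separate stopping study drug from leaving the study, so the same event can lead to different follow-up before Day 168

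*Combined protocol and SAP*

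**What the plan says.** Section 7.1 covers stopping study drug: "Discontinuation from study intervention does not mean discontinuation from the study", and what is left of the schedule is still to be carried out under the protocol. Its reasons include disease progression, and investigator discretion by reference to 6.4, 6.5 and 7.2.

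Other sections describe what follows a stop in different terms:

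- **6.1.2:** a flare that is still worsening at re-evaluation leads to withdrawal from the study. The neutrophil and hemoglobin rules say only that the participant is withdrawn under Section 7.
- **6.3:** after unblinding for clinical care, "Such participant(s) would be withdrawn from the study and followed up as described in section 4.10 above". Section 4 ends at 4.3.
- **6.4:** compliance below 80% leads to withdrawal from the study, and "Participants withdrawn from the study after receiving study treatment will be asked to follow up to complete the study days 168 and 196".
- **6.6:** the need for a prohibited medication ends study treatment; then "Withdrawn participants will be asked to return according to the follow up phase of the study and to complete all study procedures".
- **7.2:** before removal from the study, "effort must be made to have all subjects complete a safety visit approximately 14 days (+14 days) following the last dose of study therapy". It also lets a participant stop treatment and stay in follow-up. However, one list of reasons serves both withdrawing treatment and withdrawing the participant, and it does not say which reason leads to which.
- **8.2.2:** those who leave or are taken off the study after dosing "will be asked to complete the day 168 and 196 for close out safety assessments".

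**The concern.** The protocol recognises two states, off drug but on study and off study, yet it does not assign stopping reasons to them. Two staff members who follow the text could give the same participant different visit schedules.

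This matters for three reasons.

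- **Primary endpoint.** Sections 9.1 and 9.3.2 count AEs and Sjögren's flares, and 8.6.4 defines a flare partly by a rise in ESSDAI. Flares, some Grade 4 events and persistent laboratory abnormalities are themselves reasons for withdrawal in 7.2, so the missing follow-up is plausibly related to outcome.
- **Analysis sets and windows.** Section 8.7.4 closes AE recording 7 days (SAEs 30 days) after the *last day of study participation*. That day is undefined for someone taken off study but asked back at Days 168 and 196. Section 9.2.1 requires a completed *safety follow-up* for the safety population, without saying whether this is the 7.2 visit, Day 168 or Day 196.
- **Secondary analysis.** Section 9.3.3 uses the ITT population and linear mixed models for repeated measures, which draw on the intermediate visits. Section 9.3 names no missing-data method.

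**Working it through.** **1. Do the states overlap?** The same event, read under each section:

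| Event | Read as off drug, on study | Read as off study |
|---|---|---|
| Worsening disease | 7.1 (disease progression); 7.2 permits it | 6.1.2; 7.2 permits it |
| Non-compliance | 7.1 (through its reference to 6.4); 7.2 permits it | 6.4; 7.2 permits it |
| Prohibited medication | 6.6 (treatment ends, all procedures asked for); 7.2 permits it | 7.2 permits it; 6.6 also calls these participants withdrawn |
| Unblinding for care | not stated | 6.3, with a schedule that cannot be found |

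They overlap in three of the four rows. In the fourth, the schedule is a dead reference.

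**2. Which scheduled visits depend on the classification?** Section 8.2.1 places on-site visits at Days 14, 28, 56, 84, 112, 140, 168 and 196. From Day 28 on, each includes AE review, laboratory tests, ESSDAI and PGA. Under 7.1 all visits after the last dose remain; under 6.4 and 8.2.2 only Days 168 and 196 are requested. The documents give no withdrawal times, so the last-dose days below are assumptions, and a visit on the last-dose day is taken as done.

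| Last dose | On-site visits before Day 168 not requested if off study | Number | 7.2 safety window (last dose + 14 to + 28) |
|---|---|---|---|
| Day 14 | 28, 56, 84, 112, 140 | 5 | Days 28–42 |
| Day 28 | 56, 84, 112, 140 | 4 | Days 42–56 |
| Day 56 | 84, 112, 140 | 3 | Days 70–84 |
| Day 84 | 112, 140 | 2 | Days 98–112 |
| Day 112 | 140 | 1 | Days 126–140 |
| Day 140 | none | 0 | Days 154–168 |

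The counts leave out the 7.2 safety visit, whose content is not specified, and the telephone calls.

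**3. How long is the gap?** Take a last dose on Day 30 as an example. The 7.2 visit falls on Days 30 + 14 = 44 to 30 + 28 = 58. The longest gap is then from that visit to Day 168: 168 − 58 = 110 to 168 − 44 = 124 days.

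**4. How many participants?** Section 7.2 expects about 25% withdrawal and plans 30 + 11 = 41. Inflating 30 for 25% loss gives 30 / (1 − 0.25) = 40, close to 41; section 4.1 says the 11 extra places also serve to complete unfilled randomization blocks. The number withdrawn is then 0.25 × 30 = 7.5 or 0.25 × 41 = 10.25.

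**The case against.** The strongest reply is that these rules govern different states. Section 7.1 is about stopping drug, while 6.4 and 8.2.2 are about leaving the study, and 7.2 names both. Much of this stands, and it rules out several stronger readings that a reader might infer:

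- **That the schedules are mutually exclusive.** They are not. The 7.2 visit can be added to Days 168 and 196, and 7.2 leaves staying on study open for each listed reason.
- **That visits are lost as a rule.** Section 6.6 asks for all study procedures, which includes a flare needing disallowed immunosuppression. Visits drop out only for those classed as off study with a last dose before Day 140.
- **That the Day 168 comparison is lost.** Day 168 is requested wherever the text resolves. The remaining doubt is that 8.2.2 calls it a close-out safety assessment, so scoring of ESSDAI and PGA there is not assured.
- **That AEs go unassessed for about 4.5 months after a Day 30 stop.** That is the full 168 − 30 = 138 days and ignores the 7.2 visit. AE review also covers interim history (8.2.5), AEs are followed to resolution (8.7.4), and unscheduled visits exist.
- **That about 10 participants will be affected.** That would need every withdrawal to be classed as off study, after dosing, before Day 140, and not a withdrawal of consent.

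The reply fails on the central point, because 7.1 itself lists disease progression and points to 6.4 and 7.2. The two states share triggers, and the text does not say which applies. Recall at Day 168 also cannot replace scheduled laboratory tests, or an ESSDAI that by 8.2.6 reflects the preceding 28 days.

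**Conclusion.** The point holds as a failure to define two follow-up states. Depending on how a stop is classified, between 5 and 0 scheduled on-site visits before Day 168 are not requested for an assumed last dose between Day 14 and Day 140. At the protocol's own 25% rate, at most about 7.5 of 30 to 10 of 41 participants are affected. This is an upper bound, because neither withdrawal times nor classes are given.

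At risk are intermediate AE, laboratory, ESSDAI and PGA data, the end of the AE window, and entry to the safety population. The Day 168 visit itself is not at risk, only the certainty that ESSDAI and PGA are scored there. The matter should be corrected: the stops concerned are plausibly outcome-related, the primary endpoint is safety, and the remedy is cheap.

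**What to change.** Reconcile 6.1.2, 6.3, 6.4, 6.6, 7.1, 7.2 and 8.2.2 with one visit schedule per state:

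- Unless consent is withdrawn, a participant who stops drug stays on study for the remaining scheduled AE, laboratory, ESSDAI and PGA visits, with ESSDAI and PGA named explicitly at Day 168.
- Keep the 7.2 safety visit for those who do leave the study.
- Define *last day of study participation* (8.7.4) and *safety follow-up* (9.2.1).
- Replace the reference to section 4.10 in 6.3. In the same pass, correct the reference in 8.2.2 to Section 16.1.8, since the document ends at Section 13.

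No rule on when to stop drug changes.

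The cost is amendment wording and a few visits that are already in the schedule, which some participants may decline. Section 10.4 limits telehealth to extreme situations, so routine remote visits would need their own wording. The synopsis gives an end date of 09/20/2024 against a version date of 07/01/2024, so added visits can help only participants still being followed. The definitions are needed for the analysis of all participants.

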7.2 PARTICIPANT DISCONTINUATION/WITHDRAWAL FROM THE STUDY

Prior to removal from study, effort must be made to have all subjects complete a safety visit approximately 14 days (+14 days) following the last dose of study therapy. Participants are free to withdraw consent at any time upon request. Participants may also choose to withdraw treatment but remain in the study for follow up. Participants must be withdrawn consistent with Section 6.1.2. Additionally, the PI or Medically Responsible Investigator may also choose to withdraw treatment or withdraw a participant from the study based on clinical or professional judgement. An investigator may withdraw treatment or a participant from study for the following reasons:

- Request by participant to be withdrawn from the study.
- Flares not resolving within 28 days or if, in the opinion of the medically-responsible investigator, the participant requires immediate immunosuppressive therapy that is not allowed in the protocol.
- Any Grade 4 adverse event that is unexpected and at least possibly related to study drug.
- More than 45 days delay in treatment after the screening visit.
- More than one (1) "no-show" for a visit.
- Persistent elevation of LFTs of > 2 times upper limit of normal persistently present on repeated samples 14 days +/- 7 days apart.

- >30% increase in serum creatinine from baseline at enrollment, persistently present on repeated samples 14 days +/- 7 days apart.
- Increase in proteinuria at the time of screening visit to protein to creatinine ratio of more than 1.000 mg/dL or more than 1000 mg in a 24 hours urine collection, persistently present on repeated samples 14 days +/- 7 days apart.
- Any other reason that, in the opinion of the responsible Investigator or Medically Responsible Physician, poses unacceptable risk to the participant.
- Infections requiring intravenous antibiotic treatment.
- Development of any malignancy.
- Urine BK virus level of more than 10 million copies/ml by quantitative PCR or detection of BK virus in serum by quantitative PCR.
- Non-compliance with treatment (<80% compliance by pill count).

The reason for participant discontinuation or withdrawal from the study will be recorded on the Voluntary Study Withdrawal Case Report Form (CRF). Participant who signs informed consent and are randomized, but do not receive the study drug, may be replaced.

Participants who sign informed consent, and are randomized and receive the study intervention, and subsequently withdraw, or are withdrawn from the study, will be replaced.

A Participant is considered to have completed the study when he/she has completed 168 days of treatment with Tofacitinib and the day 196 follow-up assessments.

Participants randomized to a study arm who withdraw from the trial prior to starting on study drug will be replaced. Participants who withdraw study treatment and/or withdraw from the trial for any reason other than drug related adverse events after initiating the first dose of Tofacitinib and before completing 112 doses of Tofacitinib (study day 56) will also be replaced in order to maintain the sample size of 20 participants on Tofacitinib and 10 participants on placebo, for total of 30 evaluable participants. Based on experience with studies in SS participants, we expect a withdrawal rate of approximately 25% and therefore plan for a target enrollment of 30 participants plus 11 participants in event of participant withdrawal.

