1.2 SCHEMA

1.3 SCHEDULE OF ACTIVITIES (SOA)

Procedures	SCR – Visit 1 -45 days to Day 1*	Baseline Visit 2 D 1	D7 t/call (+/- 3 days)	Visit 3 D 14	D21 t/call (+/- 3 days)	Visit 4 D 28	D42 t/call (+/- 3 days)	Visit 5 D 56	D70 t/call (+/- 3 days)	Visit 6 D 84	Visit 7 D 112	Visit 8D 140	D154 t/call (+/- 3 days)	End of Tx. Visit 9 D 168	End of Study Visit 10 D 196	UNSCH visit: AE or other reason
Informed Consent	X															
Review of inclusion and exclusion criteria	X															
Vital sign measurements	X	X		X		X		X		X	X	X		X	X	X
Dental History and Oral and Head and Neck Exam	X	X								X				X	X	
Saliva Collection	X	X								X				X	X	
Salivary Flow Rate	X	X								X				X	X	
Oral Microbiome/ Plaque Collection		X												X		
Salivary Gland Ultrasound	X									X				X		
Comprehensive Ophthalmic Examination, Schirmer's test	X (with fundoscopy and MMP-9)									X				X (with MMP-9)	X	
EKG	X	X												X	X	X
Concomitant medications review.	X	X	X	X	X	X	X	X	X	X	X	X	X	X	X	X
Minor Salivary Gland Biopsy	X													X		
Presenting Symptoms- Abbreviated Medical History and physical examination	X	X		X		X		X		X	X	X		X	X	X
Complete blood count with differential	X	X		X		X		X		X	X	X		X	X	X
Blood/serum chemistries: (creatinine, glucose, urea nitrogen, total bilirubin, alanine aminotransferase, aspartate aminotransferase, alkaline phosphatase, albumin)	X	X		X		X		X		X	X	X		X	X	X
Pregnancy test (serum or urine; for females with reproductive potential only)	X	X		X		X		X		X	X	X		X	X	X
Urinalysis and Random urine Protein/Creatinine ratio	X	X		X		X		X		X	X	X		X	X	X
BK virus quantitative PCR- urine and blood	X	X		X		X		X		X	X	X		X	X	X
Lipid Panel low density lipoprotein (LDL), high density lipoprotein (HDL), triglycerides (TG) and total cholesterol(TC)	X	X								X				X	X	X
Lipoprotein Profile (Apolipoprotein A-1 Apolipoprotein B)	X	X								X				X	X	X
Lymphocyte pheno-TBNK		X								X				X	X	X
Inflammatory Markers (hs-CRP, ESR)		X				X		X		X	X	X		X	X	X

Abbreviated Title: Tofacitinib in Sjögren's syndrome**Version Date:** 07/01/2024

Procedures	SCR Visit 1 -45 days to Day 1	Baseline Visit 2 D 1	D7 t/call (+/- 3 days)	Visit 3 D 14	D21 t/call (+/- 3 days)	Visit 4 D 28	D42 t/call (+/- 3 days)	Visit 5 D 56	D70 t/call (+/- 3 days)	Visit 6 D 84	Visit 7 D112	Visit 8 D 140	D154 t/call (+/- 3 days)	End of Tx. Visit 9 D168	End of Study Visit 10 D196	UN SCH visit: AE or other reason

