5.2 EXCLUSION CRITERIA

In order to be eligible to participate in this study, an individual must not meet any of the following criteria:

1. Current or prior treatment with rituximab, belimumab or any other biologic agent in the 6 months prior to screening.
2. Current treatment with methotrexate, azathioprine, mycophenolate mofetil, cyclosporine, tacrolimus, or other less common immunomodulatory drugs such as those falling into the class of disease-modifying antirheumatic drugs (DMARDs), not otherwise specified herein. Participants previously on methotrexate, azathioprine, mycophenolate mofetil, cyclosporine or tacrolimus, or other DMARDs should have withdrawn drug for at least 8 weeks (56 days) at the time of screening.
3. Treatment with cyclophosphamide, pulse methylprednisolone or IVIG within 6 months prior to screening.
4. Current treatment with potent inhibitors of Cytochrome P450 3A4 (CYP3A4) (e.g., ketoconazole) or receiving one or more concomitant medications that result in both moderate inhibition of CYP3A4 and potent inhibition of CYP2C19 (e.g., fluconazole) that would increase serum availability of Tofacitinib. Past treatment with the aforementioned agent is allowed if it was more than a week prior to the administration of the first dose of study medication.
5. History of chronic liver disease, not including well-controlled Sjogren's-related chronic liver disease or elevated LFTs:
 - ALT or AST \geq 2x upper limit of normal at screening
 - Serum unconjugated bilirubin $>$ 2mg/dL at screening
6. Serum creatinine $>$ 1.5mg/dL.
7. Protein to creatinine ratio of more than 1mg/dL at screening (repeated and confirmed three times or confirmed with 24 hours urine protein of more than 1000 mg).
8. Active urinary sediment (WBC, RBC or mixed cellular casts 1+ or more /hpf).
9. Hypercholesterolemia: Values after 8-12 hour fasting blood specimen: total cholesterol $>$ 250 mg/dL or LDL $>$ 180 mg/dL or hypertriglyceridemia (triglyceride $>$ 300 mg/dL) within - 45 days of screening visit.
10. WBC $<$ 2500/ μ L or ANC $<$ 1,000/ μ L, Hgb $<$ 9.0 g/dL or platelets $<$ 70,000/ μ L or absolute lymphocyte count $<$ 500/ μ L.
11. Pregnant or lactating women. Women of childbearing potential are required to have a negative pregnancy test at screening.
12. A history of drug or alcohol abuse within the 6 months prior to screening.
13. Currently receiving hemodialysis, peritoneal dialysis, or intestinal dialysis.

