10.5 OUTPATIENT/OUTSIDE CLINICAL LABORATORY TESTING

Outpatient/Outside Clinical Laboratory Testing may be performed by local CLIA-certified laboratories for study visits for non-local participants that are unable to have laboratory testing performed at the NIH. Participants will be given a laboratory order by the NIH health team to be used at their local CLIA-certified laboratory. Participants and the CLIA-certified lab will be instructed to have lab results sent to NIH via fax within 7 business days (\pm 7 days) to the research team. Additional outpatient blood or urine tests may be ordered as clinically indicated. Lab work to be obtained at local CLIA-certified lab will follow required protocol visit labs.

BLOOD SPECIMENS FOR RESEARCH ASSAYS WILL NOT BE PERFORMED BY OUTSIDE LABORATORIES. FOR REMOTELY COMPLETED SAFETY LABS NOT COVERED BY THE PATIENT'S INSURANCE, WE WILL COVER THE COST FOR COMMERCIAL LABORATORY TESTING.

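### The protein-to-creatinine limit is given in mg/dL in exclusion 7 and Section 7.2, a unit a ratio cannot have, and the 7.2 bullet ties the increase to screening instead of measuring it from screening

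*Combined protocol and SAP*

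**What the plan says.** Section 5.2, exclusion criterion 7, bars entry for a "Protein to creatinine ratio of more than 1mg/dL at screening". The finding must be "repeated and confirmed three times or confirmed with 24 hours urine protein of more than 1000 mg".

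Section 7.2 lists reasons for which an investigator may withdraw treatment or a participant. One is "Increase in proteinuria at the time of screening visit to protein to creatinine ratio of more than 1.000 mg/dL", which continues "or more than 1000 mg in a 24 hours urine collection, persistently present on repeated samples 14 days +/- 7 days apart". The bullet just before it concerns renal function and names its reference point: a rise of more than 30%, worded as "increase in serum creatinine from baseline at enrollment".

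The Schedule of Activities (Section 1.3) lists "Urinalysis and Random urine Protein/Creatinine ratio" at screening and at every planned on-site visit. Section 10.5 lets non-local participants who cannot be tested at the NIH use a local laboratory, and says "Lab work to be obtained at local CLIA-certified lab will follow required protocol visit labs".

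No other section corrects the unit or the time reference.

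**The concern.** There are two faults in the wording.

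- **Unit.** Both limits are written as a concentration, but the quantity is a ratio. Exclusion 6, directly above exclusion 7, uses mg/dL correctly for serum creatinine, which is a concentration. Section 7.2 also writes the number with three decimals. Without a valid unit, it could be read as one or as one thousand.
- **Timing.** A withdrawal rule should describe something that happens after entry. This bullet attaches the increase to the screening visit, where a confirmed high value is already an exclusion.

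Safety is the primary endpoint, and the protocol itself raises renal concerns: BK virus nephropathy (Section 2.3.1) and creatinine rises (Section 2.4.1). An investigator holding a reported ratio should be able to compare it directly with the limit. Which participants are withdrawn can also affect who is replaced under Section 7.2, so the rule should be applied consistently in a trial of 30.

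**Working it through.** No power, alpha or event count depends on this point. The check is of units, value and timing.

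**Unit.** Protein in mg/dL divided by creatinine in mg/dL cancels to mg/mg, which is dimensionless. Multiplying by 1000 gives mg/g, so 1 mg/mg = 1000 mg/g. The unit mg/dL is therefore invalid in both places.

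**Intended value.** Each ratio limit stands beside a 24-hour limit of 1000 mg. The matching ratio is

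ratio (mg/mg) = 1000 mg protein per day ÷ creatinine excretion in mg per day.

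The documents give no creatinine excretion, so these values are assumptions:

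| Assumed creatinine excretion | Ratio matching 1000 mg per 24 h |
|---|---|
| 600 mg/day | 1000/600 = 1.67 mg/mg |
| 1000 mg/day | 1000/1000 = 1.00 mg/mg |
| 1800 mg/day | 1000/1800 = 0.56 mg/mg |

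A limit of about 1 mg/mg fits. The spread reflects differences between people in creatinine excretion and does not measure the error; it would remain after correction.

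**Agreement of the two limits.** As a ratio in mg/mg, 1 and 1.000 are the same. If the 7.2 figure is read as one thousand, it matches exclusion 7 only when expressed in mg/g, since 1000 mg/g = 1 mg/mg. In a common unit, that reading would put the two limits apart by a factor of 1000. The 24-hour figures rule this out as the intention, but the reader has to work that out.

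**Timing.** The relevant texts compare as follows:

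| Item | What it describes | Time reference |
|---|---|---|
| Exclusion 7 | Ratio above the limit, confirmed | At screening |
| 7.2 creatinine bullet | Rise of more than 30%, persistent | From baseline |
| 7.2 proteinuria bullet | Increase to above the limit, persistent | At the screening visit |

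On its literal words the third row largely duplicates the first. That a rise from screening was meant is an inference. It rests on the purpose of the list, on the neighbouring bullet, and on the repeat-sample rule, which differs from the confirmation rule in exclusion 7.

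**Use on study.** The Schedule of Activities lists the ratio at screening and Days 1, 14, 28, 56, 84, 112, 140, 168 and 196, which is 10 planned visits. Seven follow the first dose and fall no later than Day 168: Days 14, 28, 56, 84, 112, 140 and 168.

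**The case against.** The strongest reply is that this is editorial. Each ratio limit is paired with a 24-hour limit in a valid unit, so a usable threshold is already on the page. Unlike the creatinine rule, which is relative and needs a baseline, the proteinuria limit is absolute. Because exclusion 7 bars confirmed high values, a later persistent value above the limit would generally be an increase anyway. The 7.2 list also contains a pre-dose rule on delay after screening, so a screening-period reading is not absurd.

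Other text covers action on proteinuria. The Day 1 procedures in Section 8.2.1 withhold drug for a medically significant abnormal ratio and remove the participant if it does not resolve. Section 7.1 allows discontinuation for a laboratory abnormality, and Section 8.6.4 requires laboratory results to be evaluated. The NIH laboratory is central (Section 8.2.11), and nothing says that an outside laboratory's report would be misread.

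Much of this stands, and it limits the seriousness. The creatinine bullet is a model for naming a reference point, not an identical kind of rule. The outside-laboratory argument is secondary. But the Day 1 rule gives no number and applies only to that visit, and Sections 7.1 and 8.6.4 give no proteinuria limit. The permissive list and the general clauses give discretion; they do not supply a correctly written, specific threshold for a rise on treatment.

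**Conclusion.** The concern holds. The unit is wrong in both places, and as written the 7.2 bullet does not describe a rise during treatment. The unit error follows from the definition of a ratio and needs no assumption. The intended value of about 1 mg/mg is inferred from the adjacent 24-hour limits, with creatinine excretion near 1 g/day assumed. The intended reference to a rise from screening is also an inference, though a well supported one.

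The effect is small: no endpoint, analysis population, sample size or test changes. It should still be corrected, because these are decision thresholds for entry and withdrawal in a trial whose primary endpoint is safety.

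**What to change.** - **Exclusion 7:** state the limit as a protein-to-creatinine ratio above 1 mg/mg (1000 mg/g). Keep the existing confirmation rule.
- **Section 7.2:** describe an increase in proteinuria *from* the screening visit to a ratio above 1 mg/mg (1000 mg/g), or to above 1000 mg in a 24-hour collection. Keep the existing repeat-sample rule.
- **Confirmation:** the sponsor's clinicians should confirm the value, and whether screening or Day 1 is the reference.

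The cost is two lines of wording, with no new test, visit or analysis. Under the Statement of Compliance an amendment also needs IRB approval. This version is dated 07/01/2024 and the synopsis gives an end date of 09/20/2024, so the change is most sensibly made with any other amendment in hand.
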